### **1.0 Background & Rationale**

---

The success rate for pulpal anesthesia in mandibular molars diagnosed with symptomatic irreversible pulpitis has been shown to be between 45-70% (1). While the specific mechanism for inadequacy is unknown, it has been proposed that expression of variable sodium channels during inflammation, changes in tissue pH and, peripheral blood flow may contribute (2). OnPharmaTM offers a solution to increase the efficacy of local anesthetics by allowing the clinician to add a buffering agent to the solution prior to injection.

The OnPharmaTM system adds sodium bicarbonate to the anesthetic solution to raise its pH to a level closer to the anesthetics pKa. In doing so, more of the free base form is present to

diffuse through cell membranes. The free base is the active ingredient in local anesthetic solutions that are responsible for analgesia. In addition, CO2 and water are produced through the addition of sodium bicarbonate to the anesthetic solution. CO2 converts the local anesthetic back into its active acid form once inside the cell membrane, trapping the local anesthetic inside (2,3).

Recent studies have suggested that buffered anesthetics do not improve Inferior alveolar nerve block (IANB) success rate in symptomatic teeth (4,5,6). This contrasts with another study showing increased success with sodium bicarbonate use with IANB blocks (7). While the field is not currently in agreement, Indiana University School of Dentistry (IUSD) has had a positive experience when using the OnPharmaTM system to anesthetize symptomatic teeth.

[name], a previous resident of Indiana University Endodontics, investigated the efficacy of buffered and plain 2% lidocaine with 1:100k epinephrine. His data suggest that there is not a significant difference between the two when treating mandibular molars diagnosed with symptomatic irreversible pulpitis. This current iteration aims to investigate the synergistic ability of a combination of buffered anesthetics to improve patient analgesia. Previous studies have reported that a local infiltration of articaine with a IANB of lidocaine improve local anesthetic success rates in patients diagnosed with symptomatic irreversible pulps (8,9). Carbocaine performs as well as lidocaine when used solely for an IANB but current data suggests it does not improve anesthesia when combined with other anesthetics (10,11).

This study will include the administration of 1.8mL of 2% Lidocaine with 1:100k epinephrine and 1.8mL of 3% Carbocaine through an IANB. 1.8 mL of 4% Articaine with 1:100k epinephrine will also be used to locally infiltrate. The anesthetic combination will either be unbuffered or buffered using the OnpharmaTM protocol and will administered in a double blinded fashion.

Investigational Products:

2% Lidocaine with 1:100k epinephrine (Septodont Inc, New Castle, DE). A standard carpule of Lidocaine contains 1.8mL of solution. 1 carpule will be administered via a IANB of 2% Lidocaine w/ 1:100k epi as the standard anesthetic dosage.

3% Carbocaine without epinephrine (Septodont INC, New Castle, DE). Each carpule contains 1.8mL of solution. This will be administered via an IANB.

4% Articaine with 1:100k epinephrine (Septo Inc, New Castle, DE). A standard carpule contains 1.8 mL of solution. This will be used as a local infiltration.

The Onset 8.4% Sodium Bicarbonate buffering system is marketed by OnPharma (Carson City, NV). Aside from the sodium bicarbonate buffer itself, OnPharma offers the Onset Mixing Pen along with an Onset Cartridge Connector which formulates the buffered local anesthetic solution. The OnPharma mixing protocol will be used to mix each anesthetic prior to administration.

Vitality Scanner 2006 (Vitality Scanner 2006; SybronEndo, Orange, CA) is marketed and sold by Kerr Dental, and will be used to confirm pulpal anesthesia via Electric Pulp Testing (EPT).

Endo-Ice (1,1,1,2 tetrafluoroethane; Hygenic Corp, Akron, OH) will be used to diagnose each tooth prior to treatment and once again to confirm pulpal anesthesia.

**2.0      Objective(s)**

**2.1      Primary Objective**

**2.1.1** The primary objective of this study is to determine whether pulpal anesthesia will be obtained faster and more profoundly compared to using unbuffered local anesthetic in teeth diagnosed with symptomatic irreversible pulpitis.

**2.2      Secondary Objective**

**2.2.1** To measure a potential difference in the buffered anesthetic's effect on time and profoundness in achieving pulpal anesthesia between mandibular first, second, or third molars diagnosed with symptomatic irreversible pulpitis

**3.0      Outcome Measures/Endpoints**

**3.1      Primary Outcome Measures**

**3.1.1** The primary outcome is to gauge the time it takes for the buffered anesthetic to provide profound anesthesia, displayed by an EPT reading of 80. The time will be censored at 15 minutes if profound anesthesia is not achieved within 15 minutes.

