### **4.2 Exclusion Criteria**

- Patients lacking a response to cold in the affected tooth
- A radiographic periradicular pathosis more advanced than a widened periodontal ligament (radiograph taken as standard of care)
- No vital coronal pulp tissue noted upon access
- Patient reported pain (other than pressure) upon endodontic access/pulpotomy

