7. Administer **1 carpule** (1.8mL) of the previously determined formulation of 2% Lidocaine w/ 1:100k epi and 1 carpule of 3% Carbocaine plane via IANB, followed by 0.5 carpules (0.9mL) of 4% Septocaine with 1:100k epi via buccal infiltration and 0.5 carpules of 4% Septocaine with 1:100k epi via lingual infiltration (about 3 minutes)
8. Using a stopwatch, the student researcher will wait 3 minutes after administering anesthesia and then obtain the 2nd EPT reading on the tooth being treated, as well as assessing soft tissue anesthesia of the respective side of the mandible

- a. EPT=80 (maximum stimulation) without pulpal or soft tissue sensations indicates profound pulpal anesthesia and the endodontic access may be initiated
- b. EPT $\neq$ 80 with pulpal and/or soft tissue sensations indicates a need to wait additional time
9. Retest the tooth being treated using EPT at 2-minute intervals until EPT=80 or when 15 minutes have passed
  - a. Participants who did not demonstrate total soft tissue and/or pulpal anesthesia within 15 minutes will be categorized as a failure (lack of anesthetic profoundness), with time to anesthesia censored at 15 minutes. No additional study outcomes will be collected from the patients, who will be withdrawn from the study, and further managed according to the best clinical practice (additional block/supplementary injections) so that the endodontic treatment may continue appropriately
10. Patients who indicate any pain (excluding pressure) elicited from the tooth undergoing treatment upon endodontic access or a complete pulpotomy (after initially confirming pulpal anesthesia with the EPT) will also be categorized as a failure (lack of anesthetic profoundness), withdrawn from the study, and appropriately managed as previously described.
  - a. Visual Analog Scales (VAS) shown below will be used to report the patient's perceived discomfort at the end of treatment.

11. The student researcher will chart the data for each uniquely identified study participant regarding the initial EPT readings (treated tooth and control), the amount of time taken to reach both soft tissue and pulpal anesthesia, and the conditions that lead to a "failed" profoundness of anesthesia
  - a. A trained research assistant will separately record each patient's unique identifying code with the anesthetic formulation (buffered vs. unbuffered) that was prepared and administered

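### Patients who reach EPT=80 and then feel pain on access: Section 3.1.1 makes them events, Section 11 can be read as censoring them at 15 minutes, and Section 4.2 lists them as excluded

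*Combined protocol and SAP*

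**What the plan says.** All references are to the combined protocol and SAP.

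- **Section 3.1.1.** The main endpoint is given as "to gauge the time it takes for the buffered anesthetic to provide profound anesthesia, displayed by an EPT reading of 80", with censoring at 15 minutes if this is not achieved by then.
- **Section 7.0, step 8a.** "EPT=80 (maximum stimulation) without pulpal or soft tissue sensations indicates profound pulpal anesthesia", after which access may begin.
- **Step 9.** Retesting continues "until EPT=80 or when 15 minutes have passed".
- **Step 9a.** "Participants who did not demonstrate total soft tissue and/or pulpal anesthesia within 15 minutes will be categorized as a failure", with the time expressly censored at 15 minutes. It adds: "No additional study outcomes will be collected from the patients, who will be withdrawn from the study".
- **Step 10.** Patients with pain on access or pulpotomy "after initially confirming pulpal anesthesia with the EPT) will also be categorized as a failure (lack of anesthetic profoundness), withdrawn from the study". No time or censoring rule is given for them.
- **Step 11.** The researcher charts "the amount of time taken to reach both soft tissue and pulpal anesthesia".
- **Section 4.2.** One exclusion criterion is "Patient reported pain (other than pressure) upon endodontic access/pulpotomy". Another is the absence of vital coronal pulp at access.
- **Section 11.** The same expression, failure to achieve profound pulpal anesthesia, defines both the proportion compared by chi-square and the patients censored at 15 minutes in the Kaplan-Meier and log-rank analysis.

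**The concern.** Access pain after a reading of 80 is a post-treatment outcome, and its coding in the primary analysis is left to inference. An analyst who works from 3.1.1 enters an event at the observed time. An analyst who carries a single failure flag from step 10 into Section 11 censors the same patient at 15 minutes, as though anesthesia had never been reached. An analyst who applies 4.2 deletes the patient.

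These analyses answer different questions. Event coding tests speed of onset. Censored coding tests a mixture of onset and access pain, so it can reject when onset is identical in the two arms. Deletion drops randomised patients on an outcome that treatment may affect. If the choice is made after unblinding, it could decide significance.

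A related gap concerns the event itself. Section 3.1.1 uses EPT=80 alone, while step 8a also requires no pulpal or soft-tissue sensation. A reading of 80 with soft-tissue sensation fits neither step 8a nor step 8b.

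**Working it through.** **One patient, followed through the text.** Suppose EPT=80 at 5 minutes, without sensation, then pain on access.

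| Text followed | Primary coding |
|---|---|
| 3.1.1 and step 8a | event at 5 minutes |
| Step 10 label carried into the Section 11 censoring clause | censored at 15 minutes |
| 4.2 applied as written | removed |

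Randomisation is step 5, injection step 7 and EPT testing steps 8 and 9. The pain in 4.2 can therefore be seen only after all of them. Removal also conflicts with step 10, which counts these patients as failures.

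**Inputs from Section 11.** 28 per group, HR 2.25, control median 10 minutes, two-sided 5%, log-rank. Test times from steps 8 and 9: 3, 5, ..., 15 minutes. **Assumed:** exponential onset, and every access-pain rate among patients who reach EPT=80.

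**Plan's own figure.**
- P(EPT=80 by 15 min), control: 1 − 2^(−15/10) = 0.646
- P(EPT=80 by 15 min), buffered: 1 − 2^(−2.25 × 15/10) = 0.904
- Expected events: 28 × (0.646 + 0.904) = 43.4
- Schoenfeld power: Φ(√43.4 × ln 2.25 / 2 − 1.96) = Φ(0.71) ≈ 76%

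The stated 80% is not reproduced once follow-up stops at 15 minutes. That is a separate matter; 76% serves here only as the baseline.

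**Simulation.** 40,000 trials per scenario; onset rounded up to the next test time; tie-corrected log-rank. Pain is drawn among patients with EPT=80 by 15 minutes. Each simulated trial is analysed under all three codings.

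*HR 2.25:*

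| Pain, control/buffered (assumed) | Event | Censored at 15 | Removed | Event and censored disagree |
|---|---|---|---|---|
| 2% / 2% | 76% | 72% | 75% | 7% |
| 5% / 5% | 76% | 67% | 75% | 14% |
| 10% / 10% | 76% | 58% | 74% | 23% |
| 20% / 20% | 76% | 44% | 72% | 37% |
| 20% / 10% | 76% | 74–75% | 78% | 18% |
| 30% / 15% | 76% | 75% | 80% | 21% |

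Values are rounded; repeat runs differ by up to about one percentage point.

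Making pain more likely with later onset, at the same average rate, leaves censored power at 67%, 58% and 44% for 5%, 10% and 20% pain, with disagreement of 13%, 22% and 35%. Independence of pain and onset is therefore not what drives the result.

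*HR 1 (no difference in onset), rejection rate:*

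| Pain, control/buffered (assumed) | Event | Censored at 15 |
|---|---|---|
| 10% / 10% | 5% | 5% |
| 10% / 5% | 5% | 6% |
| 20% / 10% | 5% | 8% |
| 30% / 15% | 5% | 11% |

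**Loss of patients, only if 4.2 is applied.** Of 30 enrolled per group, expected removals at 10% pain are 30 × 0.646 × 0.10 = 1.9 control and 30 × 0.904 × 0.10 = 2.7 buffered. By the binomial distribution, more than 2 removals in at least one arm has probability 67% (21% at 5% pain, 2% at 2% pain). Section 11 allows for 2 unusable per group.

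**The case against.** The best reply is that event coding is already the plan's rule. Section 3.1.1 defines the event by the reading and censors only when it is not reached. Step 9a states the censoring and step 10 omits it, while acknowledging that the EPT had confirmed anesthesia. Section 11 can be read in the 3.1.1 sense, with step 10 feeding only the secondary failure outcome. Much of this stands: event coding is the most natural reading, and a reader should not infer that the three codings are equally supported or that the plan definitely censors these patients. What remains is that Section 11, the only analysis text, uses one expression for both purposes and step 10 widens who counts as a failure. The primary objective in 2.1.1, which covers both speed and profoundness, does not settle it.

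A reader might also infer that withdrawal under step 10 means removal from the analysis, or that it plainly does not. Neither is secure. Step 9a withdraws patients and keeps them, but through an express censoring clause that step 10 lacks.

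It is also fair to say that the size rests wholly on assumed rates, and that it is small if pain is rare. The 45–70% success range in Section 1.0 does not help to fix a rate: it is not stated for this three-anesthetic regimen, and its definition of success is not given. Finally, removal costs little power at equal rates, so the case against 4.2 rests on principle.

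**Conclusion.** The inconsistency is in the text and should be fixed; confidence in that is high. Confidence in its size is limited, because the documents give no access-pain rate. Under the planning assumptions and equal pain of 2% to 20%, moving from event to censored coding lowers power from about 76% to between 72% and 44%, and changes the conclusion in 7% to 37% of trials. With unequal pain and no difference in onset, censored coding rejects about 8% (20%/10%) or 11% (30%/15%) of the time; with equal pain it stays at 5%. Applying 4.2 moves power only from about 76% to 72–75% at these equal rates, but it breaks the randomised comparison.

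A reader might infer that the ambiguity always costs power or favours one arm. The documents do not support that: at 30%/15% pain the two codings have about the same power, yet still disagree in 21% of trials.

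**What to change.** Change analysis definitions only, before unblinding. The clinical steps in 7.0 stay as they are.

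1. **Section 11.** Separate the two uses of the expression. Censor at 15 minutes only patients who do not meet the 3.1.1 event by then. Patients with access pain after meeting it keep their event time in the log-rank and Cox analyses, and count as failures under 3.2.1 in the chi-square and logistic analyses.
2. **Section 4.2.** State that access pain after randomisation does not remove a patient from the time-to-anesthesia or failure analyses. Say whether VAS is collected from these patients, since step 10 withdraws them. State how absence of vital pulp found at access is handled once a patient is randomised.
3. **Sensitivity analysis.** Add one log-rank test with access-pain patients censored at 15 minutes.
4. **Event definition.** Reconcile 3.1.1 with steps 8a and 9a so that a single definition feeds item 1. If absence of soft-tissue sensation is part of it, first confirm that the data can support it: step 9 stops retesting at EPT=80, so later resolution may not be recorded. Give the EPT=80 time its own field, because step 11 may record only one joint time.

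The cost is wording in three sections, one extra test and one data field. For patients already treated, the EPT=80 time must be checked against whatever readings were kept. The downside is that access pain is then tested in the secondary failure outcome and the sensitivity test, not in the primary analysis.

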**3.2      Secondary Outcome Measures**

**3.2.1** Failure to achieve profound anesthesia.

**3.2.2** Pain scores measured using a Visual Analog Scale (VAS).

## **4.0 Eligibility Criteria**

### **4.1 Inclusion Criteria**

[figure not shown]
- Between the ages of 18 and 80 years old
- Ability and willingness to independently consent to treatment and study participation
- Uncomplicated medical history (ASA I and II)
- No allergies to local anesthetics/sulfites (confirmed or self-reported)
- Not taking any medications that may affect the proper assessment of the anesthetic (OTC analgesics within 6 hours of treatment)
- Not requiring nitrous oxide during treatment
- No active pathology in the injection area or any other pre-existing conditions that may compromise an accurate collection of data per PI's review of current and previous 30 days of medical history
- Must be experiencing signs of irreversible pulpitis (mild, moderate, or severe) in a vital mandibular posterior tooth at the time of conducting the study

### **4.2 Exclusion Criteria**

- Patients lacking a response to cold in the affected tooth
- A radiographic periradicular pathosis more advanced than a widened periodontal ligament (radiograph taken as standard of care)
- No vital coronal pulp tissue noted upon access
- Patient reported pain (other than pressure) upon endodontic access/pulpotomy

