## 7.0 Study Procedures

### Single Visit: Screening and Study procedure

1. Review medical history (about 3-5 minutes)
  - a. If previously on file, the patient will need to verbally confirm all forms are accurate
  - b. If the patient is new to IUSD, then the proper medical history intake form will be completed and confirmed by the patient, as per standard of care
  - c. Participants will be explained what an analgesic is, and will confirm they have not taken any within 6 hours prior to study participation
2. Customary sensibility testing, specifically cold and Electric Pulp Testing (EPT), will be completed to ensure a diagnosis of symptomatic irreversible pulpitis in a mandibular molar specifically on the same day that the warranted endodontic treatment is to be rendered (about 5-10 minutes) as per standard of care.
  - a. Prospective study participants will be given brief instructions on cold and EPT usage/expectations
  - b. A vital, asymptomatic, contralateral posterior tooth (ideally molar) will undergo cold and EPT testing prior to administering anesthesia to serve as an internal control
  - c. The pulpal diagnosis will be primarily confirmed using Endo-Ice
3. Review inclusion/exclusion criteria to ensure that the subject qualifies to continue with the study (about 3 minutes)
4. Perform consenting procedures for both the Non-surgical Root Canal Therapy (NSRCT) and the research study (about 5-10 minutes)
  - a. Study participants will receive a concise explanation regarding the nature of the 2 possible anesthetic formulations and the EPT testing intervals that are expected to follow. Participants will be explicitly notified that the anesthetic formulation will not affect the overall prognosis of the endodontic treatment needing to be rendered. Once profound anesthesia is confirmed, the NSRCT will proceed as usual and customary.
5. Randomize the subject to the type of anesthetic formulation (about 5 minutes)
6. Apply topical benzocaine jelly after thoroughly drying the tissues surrounding the Inferior Alveolar Nerve Block (IANB) injection site and the buccal vestibule of the tooth to be treated (about 1 minute), as per standard of care

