## **11.0 Statistical Considerations**

The two groups will be compared for differences in the percentage of subjects who fail to achieve profound pulpal anesthesia using chi-square tests. The time needed to achieve profound pulpal anesthesia for the two groups will be compared using Kaplan-Meier survival curves and log-rank tests, with patients who fail to achieve profound pulpal anesthesia censored at 15 minutes. A logistic regression model for presence of profound pulpal anesthesia will be used to determine whether molar type (first, second, third molar) affects the group comparisons; the model will include both factors and their interaction. A similar Cox proportional hazards survival model will be used for the analysis of time needed to achieve profound pulpal anesthesia. VAS scores will be compared between treatments using a Wilcoxon Rank Sum test. A two-sided 5% significance level will be used for all tests.

With a sample size of 28 subjects per group, the study will have 80% power to detect a hazard ratio of 2.25 between the two groups for time to profound pulpal anesthesia, using calculations with a two-sided 5% significance level and based on a log-rank test with median time to anesthesia 10 minutes in the control group. Sample size calculations were performed using PASS 2019 (NCSS, LLC. Kaysville, UT). To account for up to 2 subjects per group with unusable data, the study will enroll 30 subjects per group.

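### Pain on access is an exclusion in Section 4.2 and a treatment failure in step 10, and Section 11 does not say whether or how these randomized patients are analysed

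*Combined protocol and SAP*

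**What the plan says.** Section 4.2 lists among the exclusion criteria "Patient reported pain (other than pressure) upon endodontic access/pulpotomy".

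In Section 7.0 the order is: eligibility review at step 3, "Randomize the subject to the type of anesthetic formulation" at step 5, injection at step 7, EPT readings at steps 8 and 9, and access at step 10. For a patient who has pain at access, step 10 says that such a patient, "after initially confirming pulpal anesthesia with the EPT) will also be categorized as a failure (lack of anesthetic profoundness), withdrawn from the study".

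Section 3.1.1 measures the time to "provide profound anesthesia, displayed by an EPT reading of 80" and censors at 15 minutes only when that state is not reached by then. Section 3.2.1 makes failure a secondary outcome. Section 11.0 compares failure percentages by chi-square and logistic regression, and compares times by log-rank and Cox, "with patients who fail to achieve profound pulpal anesthesia censored at 15 minutes". It does not mention pain on access, does not define an analysis population, and does not say what withdrawal means for the analysis. On losses it says only: "To account for up to 2 subjects per group with unusable data, the study will enroll 30 subjects per group".

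**The concern.** An exclusion criterion should be assessable before randomization. This one is an outcome of the treatment under test, so it cannot screen anyone. It can only remove patients who were already randomized and treated, and it removes them because the anesthetic did not work.

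Two things are at stake.

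- **Failure outcome (3.2.1).** There are two ways to fail: never reaching EPT=80, or reaching it and then having pain. If Section 4.2 is applied as written, the second is deleted. Failure is understated in both arms, and the comparison is biased whenever the formulation affects the two components differently.
- **Primary time outcome (3.1.1).** A patient who reaches EPT=80 and then has pain has had the event under 3.1.1, is a failure that could be censored at 15 minutes under step 10 with Section 11.0, and is absent under Section 4.2. If the choice is made after data are seen, the primary result is open to selection.

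**Working it through.** **The passages side by side**

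| Source | Status of a patient with EPT=80 and later pain |
|---|---|
| 3.1.1, step 8a | Event at the time of EPT=80 |
| Step 10 with Section 11.0 | Failure; could be censored at 15 minutes |
| Section 4.2 | Excluded |

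Step 9a gives patients who never reach anesthesia an explicit censoring time. Step 10 gives none.

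**The plan's own figure.** Inputs from Section 11.0: hazard ratio 2.25, 80% power, two-sided 5%, control median 10 minutes. Freedman's formula gives (1.960 + 0.842)² × (3.25/1.25)² ≈ 53.1, or 54 events after rounding up to equal arms. That is 27 per group if everyone has an event, against the stated 28. With the 15-minute cut, 28 per group yields 28 × (0.646 + 0.904) = 43.4 expected events and about 76% power. That shortfall is a separate matter. It is noted so that the baseline below is not a surprise.

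**Assumptions.** Exponential times. EPT failure at 15 minutes is f = 2^(−15/10) = 0.354 in control and 0.354^2.25 = 0.096 in the buffered arm. The documents give no pain-on-access rate, so let q be the share of patients reaching EPT=80 who then have pain, equal in both arms, from 5% to 30%. There are 30 patients per arm.

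**Failure comparison.** With all analysed, the failure rate is f + q(1 − f). After deletion it is f / [1 − q(1 − f)]. At q = 20%:

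- Control: 0.354 + 0.2 × 0.646 = 0.483 becomes 0.354 / (1 − 0.129) = 0.406.
- Buffered: 0.096 + 0.2 × 0.904 = 0.277 becomes 0.096 / (1 − 0.181) = 0.118.

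Rejection rates are by exact enumeration of the Pearson chi-square without continuity correction. Expected deletions are 30 × q × (1 − f).

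| q | Failure, all analysed (control vs buffered) | Failure, pain patients deleted | Chi-square rejection, all → deleted | Expected deletions (control / buffered) |
|---|---|---|---|---|
| 5% | 38.6 vs 14.2% | 36.5 vs 10.1% | 59% → 69% | 1.0 / 1.4 |
| 10% | 41.8 vs 18.7% | 37.8 vs 10.6% | 50% → 68% | 1.9 / 2.7 |
| 20% | 48.3 vs 27.7% | 40.6 vs 11.8% | 37% → 67% | 3.9 / 5.4 |
| 30% | 54.7 vs 36.7% | 43.9 vs 13.2% | 29% → 65% | 5.8 / 8.1 |

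These rejection rates arise under a true difference. They show that deletion changes the quantity being compared; they are not false-positive rates. The chance of more than 2 deletions in an arm (control / buffered) is 7% / 15% at q = 5% and 76% / 93% at q = 20%, against an allowance of 2.

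**False positives when total failure is equal.** Here the component rates are shares of all randomized patients, not of those reaching EPT=80. After deletion the chi-square test rejects:

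- 5% of the time if both components are equal across arms (EPT failure 30%, pain 14%);
- 10% if EPT failure is 30/20% and pain 10/20% (control/buffered);
- 44% in a stress case with EPT failure 35.4/9.6% and pain 9.6/35.4%.

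**Primary log-rank.** 40,000 simulated trials, 30 per arm, times read at the EPT checks (3, 5, …, 15 minutes), two-sided 5%.

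| Coding of step-10 patients | q = 5% | 10% | 20% | 30% |
|---|---|---|---|---|
| Event at EPT=80 | 78% | 78% | 78–79% | 78% |
| Censored at 15 minutes | 69% | 61% | 46% | 35% |
| Deleted | 77% | 77% | 75% | 73% |

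If time to EPT=80 is the same in both arms but pain differs (20% control, 40% buffered), rejection at 28 per arm is about 5% with the event coding, 7% with deletion and 16% with censoring at 15 minutes (1,500 simulated trials).

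**The case against.** The procedural text leans toward keeping these patients. Step 10 uses the same failure label as step 9a. Step 11 has the researcher chart what led to each failure. Eligibility is reviewed at step 3, and nothing in Section 7.0 tells staff to reapply Section 4.2 after access. Withdrawal does not imply removal, because step 9a patients are also withdrawn and still contribute a censored time. One can also say that 3.1.1 and step 8a already settle the primary event as EPT=80, so that step 10 bears only on the secondary outcome. On size, the pain rates are assumed, and the stress case implies pain in 14.9% versus 39.1% of patients reaching EPT=80 (0.096/0.646 and 0.354/0.904), outside the 5–30% range. Deletion moves primary power only from about 78% to 73–77%.

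Most of this stands, but only as to emphasis. Retention is the more natural reading of Section 7.0, the 44% figure should carry no weight in the conclusion, and deletion mainly harms a secondary outcome. Yet the Section 4.2 bullet remains written authority to delete, and no passage ranks step 10 above it. The primary coding is not settled either: the censoring sentence in Section 11.0 applies to failures, step 10 calls these patients failures, and 3.1.1 says they had the event.

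**Conclusion.** The concern holds and should be fixed before the analysis. The contradiction between Section 4.2 and step 10, and the conflict over time coding between 3.1.1 and step 10 with Section 11.0, follow from the text and need no assumption.

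The stronger ground is the primary outcome. At an assumed 20% pain rate, an unstated coding choice moves log-rank power from about 78% to 46%. The deletion problem is conditional on Section 4.2 governing. If step 10 governs and everyone is analysed, it does not arise. If Section 4.2 governs, the same 20% rate widens the failure difference from 20.6 to 28.8 points (48.3 − 27.7 and 40.6 − 11.8), and expected deletions exceed the allowance of 2 in both arms.

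The sizes rest on exponential times, the plan's median and hazard ratio, and pain rates that the documents do not supply. Where both failure components are equal across arms, deletion leaves the false-positive rate near 5%.

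**What to change.** 1. Delete the pain-on-access bullet from Section 4.2.
2. State in Section 11.0 that all randomized patients who received the assigned anesthetic are analysed. The one exception is the other finding in Section 4.2 that is made at access, "No vital coronal pulp tissue noted upon access": a baseline condition of the tooth, to be judged blind to assignment and reported by arm.
3. State that step-10 patients count as failures in 3.2.1, the chi-square test and the logistic model, and that withdrawal means no further study procedures, with data to that point kept.
4. Reconcile 3.1.1, step 10 and Section 11.0 on one coding for Kaplan-Meier, log-rank and Cox. One workable choice keeps the event at first EPT=80, as 3.1.1 defines it, with censoring of step-10 patients at 15 minutes as a sensitivity analysis.
5. Limit unusable data to reasons unrelated to the anesthetic outcome.

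The cost is one deleted bullet, a few sentences and one added sensitivity analysis, with no new data or patients. Reported failure percentages will be less favourable than under the Section 4.2 reading.
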